**CONFIDENTIAL**

Date: 27 January 2021  
 Version: 2.0  
 Status: Final  
 Page: 14 of 34

**Novo Nordisk**

**Table 4–3 Overview of defined data selections and observation periods**

Defined data selections or observation periods	Description
In-trial	
This represents the time period where subjects are considered to be in the trial, regardless of discontinuation of trial product.
 
The in-trial observation period starts at randomisation and ends at trial completion.
 
The date of trial completion is the date of the final scheduled follow-up visit V92.
 
For subjects not attending the follow-up visit V92, the date of trial completion will be the date of the last subject-investigator contact.

On-treatment	
This represents the time period where subjects are considered treated with the trial product.
 
It is a subset of the in-trial observation period, starting at the date of first dose of trial product and ending at the date of the last day on trial product.

Pregnancy period	
It is defined as the period from first day of pregnancy (date of conception corresponding to the first day in GW 2) or randomisation (whichever comes last) to the date of delivery.
 
The first day of pregnancy is based on the estimated gestational age from the US scan made before or at randomisation (visit 2) for subjects randomised pregnant and before or at visit 55 for subjects randomised non-pregnant and becoming pregnant in the conception period of the trial.
 
For subjects with delivery prior to the US scan the first day of pregnancy is determined by the investigator based on the estimated gestational age at the time of delivery.

Pre-pregnancy period	
It is defined for subjects randomised as non-pregnant. The period starts at randomisation (visit 2). Two different end-dates will be defined. For subjects who become pregnant the period ends at the day prior to first day of pregnancy. For subjects who do not become pregnant during the trial, the period ends at the same time as the in-trial period.

Post-pregnancy period	
This starts the day after the delivery and ends at the same time as the in-trial period.

The above definitions form the basis for combinations of periods. The on-treatment pregnancy period is e.g. the intersection between the on-treatment period and the pregnancy period.

Statistical Analysis Plan  
Trial ID: NN1250-4300  
UTN: U1111-1191-3018  
EudraCT No: 2017-000048-17

~~CONFIDENTIAL~~

Date: 27 January 2021  
Version: 2.0  
Status: Final  
Page: 15 of 34

**Novo Nordisk**

## 5 Statistical analyses

### 5.1 General considerations

Results from a statistical analysis will at a minimum be presented by the estimated treatment contrasts for the comparison between IDeg and IDet with associated two-sided 95% confidence intervals (CI) and p-values corresponding to two-sided tests of no difference.

Non-inferiority will be considered confirmed if the upper bound of the CI is strictly below 0.4%. The p-value corresponding to a two-sided test of no difference will also be reported.

The full analysis set for all pregnant women (**FASpregnant**) who contribute to the analysis will be used in the analysis of efficacy endpoints. For further details of how the subjects will be determined whether they contribute to the statistical analysis or not refer to [6.3.1.1](#). For the safety endpoints, the safety analysis set for all pregnant women (**SASpregnant**) will be used. The definition of analysis sets are given in section [4](#).

The treatment baseline value will be used in the statistical models and is defined as the latest available measurement at or before randomisation. For all subjects the treatment baseline value hence corresponds to the value obtained at the randomisation visit (visit 2) if available, or at the screening visit (visit 1). If neither of these measurements have been obtained the treatment baseline will be left missing. For subjects randomised pregnant the pregnancy baseline is derived from the treatment baseline, and the two baseline values will be identical, corresponding to the values obtained at visit 2 or visit 1.

When summarising change from baseline for effect and safety variables assessed during or after the pregnancy period, both treatment baseline and pregnancy baseline variables will be applied. First the treatment baseline described above to illustrate changes since initiation of treatment, second the pregnancy baseline to illustrate changes since early pregnancy.

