**Novo Nordisk**

The **pregnancy period** is defined as the period from first day of pregnancy (date of conception corresponding to the first day in GW 2) or randomisation (whichever comes last) to the date of delivery. The first day of pregnancy is based on the estimated gestational age from the US scan made before or at randomisation (visit 2) for subjects randomised pregnant and before or at visit 55 for subjects randomised non-pregnant and becoming pregnant in the conception period of the trial. For subjects with delivery prior to the US scan the first day of pregnancy is determined by the investigator based on the estimated gestational age at the time of delivery.

The **pre-pregnancy period** is defined for subjects randomised as non-pregnant. The period starts at randomisation (visit 2). Two different end-dates will be defined. For subjects who become pregnant the period ends at the day prior to first day of pregnancy. For subjects who do not become pregnant during the trial, the period ends at the same time as the in-trial period.

The **post-pregnancy period** starts the day after the delivery and ends at the same time as the in-trial period.

These definitions form the basis for combinations of periods. The **on-treatment pregnancy period** is e.g. the intersection between the on-treatment period and the pregnancy period.

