**Novo Nordisk**

Summaries will be based on SASpregnant and will display:

- Number of severe or BG confirmed symptomatic hypoglycaemic episodes
- Number of nocturnal, severe or BG confirmed symptomatic hypoglycaemic episodes
- Number of severe hypoglycaemic episodes
- Number of hypoglycaemic episodes according to ADA definition

Data on all hypoglycaemic episodes with onset during the pregnancy period will be presented similarly.

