#### **Hypoglycaemia during the in-trial period, the pre-pregnancy period and the post-pregnancy period**

Treatment emergent hypoglycaemic episodes with onset in the pre-pregnancy period, the post-pregnancy period as well as all treatment emergent hypoglycaemic episodes during the in-trial period will be summarised similarly as described for the hypoglycaemic events during the pregnancy period.

Data on all hypoglycaemic episodes within each of the three periods will be presented similarly.

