### **Adverse events during the in-trial period, the pre-pregnancy period and the post-pregnancy period**

Adverse events with onset in the pre-pregnancy period, the post-pregnancy period as well as all AEs during the in-trial period will be summarised as described above for AEs with onset in the pregnancy period

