**Novo Nordisk**

## 4 Analysis sets

**Table 4–1 Overview of subject analysis sets**

Subject Analysis Set	Description
Full analysis set for all women (FASall)	Includes all randomised women. Subjects in the FAS all will contribute to the evaluation “as randomised”.
Safety analysis set for all women (SASall):	Includes all randomised women exposed to at least one dose of trial product. Subjects in the SAS all will contribute to the evaluation “as treated”.

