**Table 4–2 Overview of defined analysis sets**

Defined Analysis Set	Description
Full analysis set for pregnant women (FASpregnant)	Includes all randomised women who are pregnant during the trial. Subjects in the FAS pregnant will contribute to the evaluation “as randomised”.
Per protocol analysis set for pregnant women (PPpregnant)	Includes subjects from FAS pregnant who: 
 
• Have not violated any inclusion criteria
 
• Have not fulfilled any exclusion criteria
 
• Are exposed to trial drug at least the first four weeks after randomisation or, in case of termination of pregnancy within the first four weeks after randomisation, until time of termination of pregnancy.
 
 Subjects in the PP pregnant analysis set will contribute to the analysis according to the treatment received prior to potential discontinuation of randomised treatment. This will be referred to as contributing to the evaluation “as treated”.
Safety analysis set for pregnant women (SASpregnant)	Includes all randomised women exposed to at least one dose of trial product and who are pregnant during the trial. Subjects in the SAS pregnant will contribute to the evaluation “as treated”.

The primary endpoint and secondary efficacy endpoints are analysed using full analysis set for all pregnant women.

Statistical Analysis Plan  
 Trial ID: NN1250-4300  
 UTN: U1111-1191-3018  
 EudraCT No: 2017-000048-17

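### The pre-pregnancy and in-trial safety summaries point to the pregnant-only safety set, although the pre-pregnancy period is defined to include women who never conceive; the all-women safety set is defined but never used

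*SAP*

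**What the plan says.** **The sets.** SAP Table 4-1 defines SAS_all: "Includes all randomised women exposed to at least one dose of trial product". SAP Table 4-2 defines SAS_pregnant: "Includes all randomised women exposed to at least one dose of trial product and who are pregnant during the trial". Protocol 17.2 has the same two definitions.

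**The period.** Protocol 17.2 and SAP Table 4-3 define a pre-pregnancy period for women randomised non-pregnant, with two possible end dates. One is for those who conceive. The other reads "For subjects who do not become pregnant during the trial, the period ends at the same time as the in-trial period".

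**The summaries.** Protocol 17.4.2.1 says of pregnancy-period hypoglycaemia: "Summaries will be based on SAS pregnant and will display" a list of episode counts. The next heading covers "Treatment emergent hypoglycaemic episodes with onset in the pre-pregnancy period", together with the post-pregnancy and in-trial periods; these "will be summarised similarly as described for the hypoglycaemic events during the pregnancy period". Protocol 17.4.2.2 sets SAS_pregnant as its default and names it for pregnancy-period adverse events. It then says that "Adverse events with onset in the pre-pregnancy period, the post-pregnancy period as well as all AEs during the in-trial period" are to be handled as already described. No other set is named for either group of summaries.

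**The SAP.** Section 5.1 gives the general rule, without exception: "For the safety endpoints, the safety analysis set for all pregnant women". Table 5-6 names SAS_pregnant in every row, and its hypoglycaemia row refers to protocol 17.4.2.1 as a whole. Section 5.6 names SAS_pregnant for the other assessments, and section 5.5 is marked not applicable. Appendix 2, which lists changes to the protocol's analyses, does not touch the point.

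**The concern.** The period definition and the named set do not fit together. An end date exists for women who never conceive, but no such woman can be in the set on which the period's summaries appear to be made. SAS_all is the only defined safety set that fits, and it is not mentioned again after its definition.

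Two things follow if the tables are built as written. First, a serious adverse event in a treated woman who never conceives is counted in none of the specified adverse event tables. Second, the pre-pregnancy comparison between arms is no longer between randomised groups, because it keeps only women who later conceived. The protocol gives reasons why conception may not be independent of events on treatment. Section 8.2 recommends contraception after randomisation until glycaemic control is judged reasonable. Section 6.5 withdraws a woman who, before becoming pregnant, starts a medication contraindicated in pregnancy. Neither shows a bias, but both are routes by which treatment could affect who enters SAS_pregnant.

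**Working it through.** **Step 1. Reproduce the plan's numbers (protocol 17.1).** Inputs: margin 0.4%, true difference 0, SD 0.85, one-sided 2.5%, power 80%, 10% delivering before GW 16, 10% excluded from the per protocol set, at most 1/3 randomised non-pregnant, about 50% of those conceiving.

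- Two-sample t-test: 72 per arm, 144 in total, as in Table 17-1.
- 144 / 0.9 = 160, and 160 / 0.9 = 177.8, rounded up to 178, as in Table 17-2.
- Randomised: 178 / (2/3 + 1/3 × 0.5) = 213.6, rounded up to 214, split 142 pregnant and 72 non-pregnant.

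All of these agree with the protocol.

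**Step 2. Women in SAS_all but not in SAS_pregnant** (assuming every randomised woman is treated).

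- 72 × (1 − 0.5) = 36. Check: 214 − 178 = 36.
- 36 / 214 = 16.8%; about 18 per arm.
- If conception were 30% or 70% rather than 50% (assumption, for range): 72 × 0.7 = 50.4 women (23.6% of 214), or 72 × 0.3 = 21.6 women (10.1%).

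**Step 3. Exposure.** Protocol Table 5-1 allows up to 53 weeks of treatment for conception. The ceiling is 36 × 53 / 52 = 36.7 patient-years. It gives every woman the maximum, although the protocol allows for up to 15% discontinuing treatment among those randomised non-pregnant.

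**Step 4. Illustrative share of pre-pregnancy exposure.** The documents give no mean time to conception, so 13, 26 and 39 weeks are assumptions. With 36 conceivers and 36 never-conceivers, the share contributed by never-conceivers is w / (w + t), where w and t are the mean weeks in the two groups.

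| Mean weeks before conception (t) | Never-conceivers at 53 weeks | Never-conceivers at 26 weeks (assumption) |
|---|---|---|
| 13 | 53/66 = 80% | 26/39 = 67% |
| 26 | 53/79 = 67% | 26/52 = 50% |
| 39 | 53/92 = 58% | 26/65 = 40% |

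Across these assumptions, 40% to 80% of pre-pregnancy exposure lies outside SAS_pregnant.

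**Step 5. Which reading does the text support?** On the literal reading, SAP 5.1 governs and the cross-references in 17.4.2.1 and 17.4.2.2 carry SAS_pregnant with them; the second end date and SAS_all then have no use. On the other reading, the cross-references carry only the display format, and SAS_all is intended for these periods. That reading gives every definition a purpose, but no sentence states it and the SAP's only stated rule points the other way.

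**The case against.** The best counter-argument is that no sentence expressly ties the pre-pregnancy or in-trial summaries to SAS_pregnant. The hypoglycaemia sentence sits under a pregnancy-period heading. The default in 17.4.2.2 sits under a heading on endpoints during and after pregnancy and yields to any other specification. The listed hypoglycaemia and adverse event endpoints are pregnancy-period counts, for which SAS_pregnant is right given objectives about pregnant women. This stands in part: the link runs through cross-references and a general SAP rule, and the authors may have meant SAS_all. It does not remove the conflict, because a programmer following the SAP has only SAS_pregnant to use.

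A reader might also infer more than the documents support:

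- **That the data are discarded.** They are not. Data from withdrawn women are retained and used in the trial report (protocol 18.3), deaths and severe or serious hypoglycaemia are adjudicated and reported (12.7.3), and the DMC reviews accumulating data (12.7.2).
- **That hypoglycaemia in never-conceivers is certainly untabulated.** Table 5-6 adds an in-trial summary on a full analysis set it does not identify. Elsewhere the SAP's prose usually adds that the women are pregnant when it means FAS_pregnant, so this may be FAS_all. It would supply no adverse event table.
- **That no by-arm conception count is planned.** This cannot be shown, since SAP 5.2 defers disposition to tables that are not part of the documents.
- **That about 37 patient-years will be missing.** That figure is a ceiling, and the shares in Step 4 rest on assumed times.

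**Conclusion.** The point holds as an inconsistency in the specified analysis set, and it should be corrected. Read as written, treated women who never conceive are absent from the planned pre-pregnancy and in-trial adverse event and serious adverse event tables. Whether they are also absent from the hypoglycaemia tables depends on the full analysis set meant in Table 5-6. The remaining pre-pregnancy comparison is conditioned on conception.

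The size rests on the 50% planning assumption and on all randomised women being treated. The actual number of never-conceivers cannot be derived: SAP Appendix 3 gives 188 women in FAS_pregnant, but neither document gives the number finally randomised.

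The affected summaries are descriptive. The primary HbA1c analysis, its sample size and the pregnancy-period safety endpoints do not depend on this.

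**What to change.** 1. In SAP 5.1 and Table 5-6, and in protocol 17.4.2.1 and 17.4.2.2, state that the pre-pregnancy and in-trial summaries of adverse events, serious adverse events and hypoglycaemia use SAS_all.
2. Keep SAS_pregnant for the pregnancy and post-pregnancy periods.
3. State whether the additional hypoglycaemia summary in Table 5-6 uses FAS_all or FAS_pregnant.
4. Optional: if the disposition tables do not already show it, report by arm how many of the women randomised non-pregnant conceived, so that a reader can see the selection into the pregnant sets.

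The cost is a few sentences and a run of already planned tables on a set that is already defined. No new data are needed.

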### Primary and secondary estimands

Primary estimand (“treatment policy” estimand):

- Treatment difference in last planned HbA1c prior to delivery after GW 16 between IDeg OD plus IAsp 2-4 times daily with meals and IDet OD/BID plus IAsp 2-4 times daily with meals for all randomised pregnant women regardless of actual treatment received.

The primary estimand assesses the average glycaemic difference prior to delivery after GW 16 in a population of pregnant women with T1DM, resulting from initiation of a treatment regimen with IDeg OD plus IAsp 2-4 times daily with meals including potential additional therapy as compared

Statistical Analysis Plan  
Trial ID: NN1250-4300  
UTN: U1111-1191-3018  
EudraCT No: 2017-000048-17

~~CONFIDENTIAL~~

Date: 27 January 2021  
Version: 2.0  
Status: Final  
Page: 16 of 34

**Novo Nordisk**

to initiation of a treatment regimen with IDet OD or BID plus IAsp 2-4 times daily with meals including potential additional therapy. Generalisation of this estimand depends among other things on the extent to which the treatment adherence and the potential use of additional therapy reflect clinical practice, and whether the trial population can be considered a representative sub-sample of the target population.

Secondary estimand (“If all subjects had adhered” estimand):

- Treatment difference in last planned HbA1c prior to delivery after GW 16 between IDeg OD plus IAsp 2-4 times daily with meals and IDet OD/BID plus IAsp 2-4 times daily with meals for all randomised pregnant women if all subjects adhered to treatment.

The secondary estimand assesses the glycaemic benefit a pregnant woman with T1DM is expected to achieve prior to delivery after GW 16 if adhering to a treatment regimen with IDeg OD plus mealtime IAsp as compared to adhering to a treatment regimen with IDet OD or BID plus mealtime IAsp. Generalisation of this estimand depends among other things on the extent to which the compliance to trial product administration in this trial reflects clinical practice. Only data collected prior to discontinuation of trial product will be included in the analysis.

## 5.2 Subject disposition

[Refer TFL of section 14.1.](#)

## 5.3 Primary endpoint analysis

### 5.3.1 Definition of primary endpoint

The primary endpoint is the last planned HbA1c prior to delivery after GW 16.

For subjects who have discontinued treatment and where retrieved last planned HbA1c prior to delivery after GW 16 data are not available, it may not be known whether time of delivery is after GW 16. In this case time of delivery will be assumed to be after GW 16 and last planned HbA1c prior to delivery after GW 16 will hence be imputed.

Statistical Analysis Plan  
 Trial ID: NN1250-4300  
 UTN: U1111-1191-3018  
 EudraCT No: 2017-000048-17

**CONFIDENTIAL**

Date: 27 January 2021  
 Version: 2.0  
 Status: Final  
 Page: 17 of 34

**Novo Nordisk**

### 5.3.2 Main analytical approach

**Table 5–1 Estimands under primary analysis**

Objective	Estimand category	Estimand			
		Variable/Endpoint	Population of interest	Intercurrent event strategy	Population-Level Summary Measure
Primary Objective: To compare the effect on glycaemic control of IDeg once daily (OD) plus IAsp 2-4 times daily with meals and IDet OD or twice daily (BID) plus IAsp 2-4 times daily with meals in a population of pregnant women with T1DM.	Primary	Last planned HbA 1c prior to delivery after gestational week (GW) 16. (Primary endpoint)	Full analysis set for all pregnant women	Treatment policy strategy	Mean difference in the IDeg and IDet arm.
	Secondary	Last planned HbA 1c prior to delivery after gestational week (GW) 16. (Primary endpoint)	Full analysis set for all pregnant women	If all subjects had adhered	Mean difference in the IDeg and IDet arm.

#### 5.3.2.1 Analysis of primary estimand

Available data from the in-trial period will be included regardless of whether trial product was discontinued or not.

The multiple imputation approach is done in three steps.

Statistical Analysis Plan  
Trial ID: NN1250-4300  
UTN: U1111-1191-3018  
EudraCT No: 2017-000048-17

**CONFIDENTIAL**

Date: 27 January 2021  
Version: 2.0  
Status: Final  
Page: 18 of 34

**Novo Nordisk**

## **Imputation :**

Step 1: Imputation of missing data will be done within four groups of subjects defined by randomised treatment arm and whether or not subjects discontinue treatment. It is hereby assumed that the likely values of what the missing data would have been if available, are best described by information from subjects who at the last scheduled visit prior to delivery are similar in terms of randomised treatment arm and whether or not treatment has been discontinued.

If there are 3 or less retrieved observations among discontinued subjects in a treatment group, it is infeasible to estimate a simple intercept model (including variance) and imputed separately by on-treatment and off-treatment. Instead, on-treatment factors will be included in the models. Hereby, separate means will be estimated for on-treatment and off-treatment observations, while only one joint variance is estimated. In the special case with no subjects off-treatment having HbA1c in one treatment group, an on-treatment factor will not be included in the this group but only in the other group (expecting that this group also has most missing values).

Missing data at the last scheduled visit prior to delivery after GW 16 are for each group imputed in the following steps:

An analysis of covariance (ANCOVA) will be fitted to the observed last values of last HbA1c prior to delivery after GW 16

- For subjects where HbA1c at the last scheduled visit prior to time of delivery is in the on-treatment period, the model will include region and the stratification factor as categorical fixed effects, and a pregnancy status at randomisation-by-baseline HbA1c interaction.
- For subjects where HbA1c at the last scheduled visit prior to time of delivery is not in the on-treatment period, the model will include pregnancy status at randomisation and a pregnancy status at randomisation-by-baseline HbA1c interaction. If this model cannot be fitted in case of very few retrieved observations among discontinued subjects, a model including pregnancy status at randomisation will be applied. If this model cannot be fitted either, a simple model including just the intercept will be fitted instead. If there are 3 or less retrieved observations among discontinued subjects in one or both treatment groups, this step will be skipped.
- With 3 or less retrieved observations among discontinued subjects in one of the treatment groups, the step below replaces the two steps above. For subjects with HbA1c at the last scheduled visit prior to time of delivery, the model will include on-treatment (Yes/No), region and the stratification factor as categorical fixed effects, and a pregnancy status at randomisation-by-baseline HbA1c interaction. In treatment groups having no subjects off-treatment with HbA1c, the on-treatment factor will not be included.

The estimated parameters from the analysis of covariance together with the variances of the estimates will be used to simulate 1000 data sets with imputed last planned HbA1c prior to delivery after GW 16 data for subjects missing these. Each of the 1000 datasets use one set of estimated

Statistical Analysis Plan  
 Trial ID: NN1250-4300  
 UTN: U1111-1191-3018  
 EudraCT No: 2017-000048-17

~~CONFIDENTIAL~~

Date: 27 January 2021  
 Version: 2.0  
 Status: Final  
 Page: 19 of 34

